1. SYNOPSIS	
PROTOCOL TITLE:	Post-Approval Study of the TECNIS Symfony [®] Toric Lenses
Protocol Number:	TIOL-205-STPA
STUDY TREATMENTS:	Toric Study Lenses:
	TECNIS Symfony Toric Extended Range of Vision IOL (Symfony Toric), Model ZXT300
	TECNIS Symfony Toric Extended Range of Vision IOL (Symfony Toric), Model ZXT375
	Toric Control Lens:
	 TECNIS Symfony Toric Extended Range of Vision IOL (Symfony Toric), Model ZXT150
	Other Study Lenses (may be used for fellow eyes):
	TECNIS Symfony Toric Extended Range of Vision IOL (Symfony Toric), Model ZXT225
	 TECNIS Symfony Extended Range of Vision IOL (Symfony), Model ZXR00
STUDY OBJECTIVE:	The purpose of this post-approval study is to evaluate the rates of bothersome visual symptoms in a larger population in clinical practice for the TECNIS Symfony Toric IOLs with approximately 2.0 D or more of cylinder correction at the corneal plane (Models ZXT300 and ZXT375, higher-cylinder group), compared to the Symfony Toric IOL with approximately 1.0 D of cylinder correction at the corneal plane (Model ZXT150, lower-cylinder group), and to ensure the continued safety of the approved devices.
CLINICAL HYPOTHESIS:	The rate of bothersome visual symptom items
	for the Symfony Toric IOL higher-cylinder

group.

group will be comparable to that of the lower-cylinder

OVERALL STUDY DESIGN:	
Structure:	Prospective, multicenter, bilateral, non-randomized, open-label, comparative clinical study
Number of Sites:	Up to 50 sites in the USA
Duration:	6 months; however, any subject that undergoes a lens repositioning procedure due to IOL misalignment, or
	at 6 months, will be followed through 1 year postoperatively.
Administration:	Surgeons will perform routine small-incision, cataract surgery and use the JJSV-recommended implantation systems for lens implantation. Refractive target outcomes will be emmetropia for both eyes.
Visit Schedule:	Subjects will be bilaterally implanted; the second eye is to be implanted within approximately one month after the first-eye surgery.
	All subjects will undergo a minimum of 9 visits: Preoperative for both eyes; Operative, 1-day and 1-week visits for each eye; and 1-month and 6-month visits for both eyes together. In addition, a 1-year postoperative visit will be required for subjects who undergo a lens repositioning procedure due to IOL misalignment at any time during the study, and for subjects who report

STUDY POPULATION CHARACTERISTICS:

Condition:

Bilateral cataracts with corneal astigmatism in at least 1 eye of approximately 2.00 D to 3.00 D (higher-cylinder group) or approximately 1.00 D to 1.50 D (lower-cylinder group) based on the combination of preoperative keratometric cylinder, the expected effect of surgically-induced astigmatism (SIA), use of the optional posterior corneal astigmatism (PCA) algorithm and TECNIS Symfony Toric Calculator outcomes of ZXT300 or ZXT375 (higher-cylinder group) or ZXT150 (lower-cylinder group).

Number of subjects:Up to 634 subjects will be enrolled to achieve
bilateral implantation in approximately 506 subjects,
resulting in approximately 240 evaluable subjects in
the higher-cylinder group and 240 evaluable subjects
in the lower-cylinder group at 6 months

This is a bilateral study; both eyes must be implanted with a TECNIS Symfony IOL, either toric (Models ZXT150, ZXT225, ZXT300 or ZXT375) or non-toric (TECNIS Symfony Extended Range of Vision IOL, Model ZXR00). Each eye may have a different TECNIS Symfony IOL implanted, as determined by the surgeon and the TECNIS Symfony Toric IOL calculator; however, at least one eye must be implanted with either a Symfony Toric IOL Model ZXT150 (lower-cylinder group) or a Model ZXT300 or ZXT375 (higher-cylinder group) and the fellow eye must have the same or a lower toric power. The eye with the highest toric power IOL will determine the model group.

NOTE: No site may enroll more than 25% of the enrollment total.

Inclusion Criteria (all study criteria apply to each study eye unless otherwise indicated):

- Minimum 22 years of age
- Bilateral cataracts for which phacoemulsification extraction and posterior chamber IOL implantation have been planned
- Preoperative keratometric cylinder of:
 - Approximately 2.00 D to 3.00 D resulting in a calculated lens power (using the web-based TECNIS Symfony Toric IOL Calculator) that requires implantation of a ZXT300 or ZXT375 IOL in at least one eye for the subject to be eligible for the higher-cylinder group, or

- Approximately 1.00 D to 1.50 D resulting in a calculated lens power (using the web-based TECNIS Symfony Toric IOL Calculator) that requires implantation of a ZXT150 IOL in at least one eye for the subject to be eligible for the lower-cylinder group
- The eye with the higher toric power IOL will determine the model group
- The fellow eye must be the same or a lower toric power
- Predicted residual refractive cylinder based on the TECNIS Symfony Toric IOL calculator, taking surgically-induced astigmatism into account and using the posterior corneal astigmatism option, must be ≤0.50 D for all toric eyes
- Clear intraocular media other than cataract in each eye
- Availability, willingness, ability and sufficient cognitive awareness to comply with examination procedures and study visits
- Ability to understand, read and write English in order to consent to study participation and complete study questionnaires
- Signed informed consent and HIPAA authorization

Exclusion Criteria (all study criteria apply to each study eye):

- Irregular corneal astigmatism
- Any clinically-significant corneal pathology/abnormality other than regular corneal astigmatism
- Previous corneal surgery
- Recent ocular trauma or intraocular surgery that is not resolved/stable or may affect visual outcomes
- Any clinically-significant pupil abnormalities (non-reactive, fixed pupils, or abnormally-shaped pupils)
- Subjects with conditions associated with increased risk of zonular rupture, including capsular or zonular abnormalities that may lead to IOL decentration, including pseudoexfoliation, trauma, or posterior capsule defects
- Known ocular disease or pathology that, in the opinion of the investigator, may affect visual acuity or require surgical intervention during the course of the study (macular degeneration, cystoid macular edema, diabetic retinopathy, uncontrolled glaucoma, etc.)
- Concurrent participation or participation during 30 days prior to preoperative visit in any other clinical study
- Planned monovision correction
- Patient is pregnant, plans to become pregnant, is lactating or has another condition associated with the fluctuation of hormones that could lead to refractive changes

EVALUATION CRITERIA:

The purpose of this post-approval study is to evaluate the rates of bothersome visual symptoms for the higher-cylinder Symfony Toric IOLs, Models ZXT300 and ZXT375, compared to the lower-cylinder Symfony Toric IOL, Model ZXT150. The first primary endpoint is the rate of bothersome visual symptoms

. The second primary endpoint will be the rate of those having a lot of difficulty with an activity due halos, glare or starbursts as measured in the PRVSQ.

Other endpoints are individual visual symptom ratings included in the PRVSQ, rates of IOL repositioning procedures (secondary surgical intervention) due to IOL misalignment, rates of explants due to visual symptoms, distance visual acuities, mean percent reduction in absolute cylinder, mean refractive cylinder, mean refractive cylinder compared to the preoperatively-predicted cylinder, mean spherical equivalent, spherical equivalent compared to the preoperatively-predicted spherical equivalent, percent of eyes with cylinder and spherical equivalent (MRSE) within 0.50 D and within 1.00 D of the preoperatively-predicted spherical equivalent, rates of medical and/or lens findings, and rates of other adverse events. Preoperatively-predicted values will be based upon those generated from the TECNIS Symfony Toric IOL calculator.

DATA ANALYSIS:

The key time frame for analysis will be the 6-month visit. The first primary endpoint for this study will be the rate of bothersome visual symptoms,

The second primary endpoint will be the rate of those having a lot of difficulty with an activity due to halos, glare or starbursts as measured in the PRVSQ. The primary endpoint results will be compared between higher-cylinder toric IOL subjects and lower-cylinder toric control IOL subjects at the 6-month visit. The frequency, proportion and 95% Confidence Interval (CI) will be reported for higher-cylinder and lower-cylinder control subjects. This will be done for the higher-cylinder (ZXT300 and ZXT375) and lower-cylinder (ZXT150) groups.

Descriptive statistics will be used for reporting results. Visual acuity data will be reported by acuity line achieved. For questionnaire items, the frequency and proportion for each response will be reported. For refractive data, descriptive statistics will include mean, standard deviation, median, minimum and maximum and also the percent achieving absolute values within 0.50 D and 1.00 D of preoperatively-predicted values.

The frequency and proportion of primary and fellow eyes with adverse events or medical/lens findings will also be reported.

STUDY VISITS AND PROCEDURES:

Inclusion and exclusion qualifications will be assessed at the preoperative visit according to the inclusion/exclusion criteria. The Informed Consent Document and Authorization for Use/Disclosure of Health Information form (HIPAA authorization) must be signed by any patients who agree to participate in the study prior to undergoing any study-specific procedures. Each subject will receive Symfony IOLs in both eyes, according to the TECNIS Symfony Toric IOL calculator, and will be placed in either the higher-cylinder group or the lower-cylinder control group based on the IOL with the highest toric power.

[figure not shown]
Key preoperative data include ocular health and history, distance visual acuities, manifest refraction, keratometry, biomicroscopic slit-lamp findings, ocular symptoms and biometry. The operative visit will include standard procedures for cataract surgery and IOL implantation. Key postoperative data collection includes non-directed visual symptoms, questionnaires, distance visual acuities, manifest refraction, keratometry, slit-lamp findings and adverse events.

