3. CLINICAL HYPOTHESIS

The rate of bothersome visual symptom items

for the

Symfony Toric IOL higher-cylinder group will be compared to the rate for the lower-cylinder group. The bothersome visual symptom items of interest are halos, glare, and starbursts.

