6. STUDY OBJECTIVES AND ENDPOINTS

The objective of this post-approval study is to evaluate the rate of bothersome visual symptoms

at 6 months for the Symfony Toric IOLs with approximately 2.0 D or more of cylinder correction at the corneal plane (Models ZXT300 and ZXT375) in a larger population in clinical practice compared to the control IOL (Symfony Toric Model ZXT150 IOL), and to ensure the continued safety of the approved devices.

Study endpoints will be evaluated at 6 months postoperatively.

6.1 **PRIMARY ENDPOINT:**

The primary co-endpoints are the rate of bothersome visual symptoms and the rate of difficulty with an activity due to the symptoms at 6 months postoperative.

The rate of difficulty with an activity due to the symptoms is determined by the percentage of subjects who respond "Yes" to the question "Is there anything you have a lot of difficulty with, or do not do, because of (visual symptom) at 6 months postoperative.

The frequency and proportion of subjects reporting one or more of these items

via PRVSQ questionnaire will be used to

determine the primary endpoint. This rate will be calculated for the higher-cylinder (ZXT300 and ZXT375) and lower-cylinder (ZXT150) groups.

6.2 OTHER ENDPOINTS:

- Other questionnaire responses, such as rates of degree of bother
- Rates of IOL repositioning procedures (secondary surgical intervention) due to IOL misalignment
- Rate of explants related to visual symptoms
- Rates of other adverse events
- Monocular uncorrected distance visual acuity
- Monocular best corrected distance visual acuity

- Mean percent reduction in absolute cylinder
- Mean refractive cylinder and mean refractive cylinder compared to preoperatively-predicted cylinder
- Mean spherical equivalent and mean spherical equivalent compared to preoperatively-predicted spherical equivalent
- Percent of eyes with absolute cylinder within 0.50 D and within 1.00 D of preoperatively-predicted cylinder
- Percent of eyes with spherical equivalent within 0.50 D and within 1.00 D of preoperatively-predicted spherical equivalent
- Rates of medical and/or lens findings

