## 7 SAMPLE SIZE CALCULATIONS

With a sample size of 240 subjects and assuming a 20% rate of bothersome visual symptoms or difficulty with an activity due to visual symptoms, a two-sided 95% confidence interval will estimate the observed rate of bothersome visual symptoms to within 4.2 percentage points.

To achieve 240 higher-cylinder group subjects and 240 lower-cylinder group subjects evaluable at 6 months, assuming an initial 20% screen-fail rate and a 5% lost-to-follow-up rate, up to 634 total subjects will be enrolled.

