### APPENDIX I: TABLE LISTING

**TIME FRAME**: The 6-month postoperative visit is the key timeframe for reporting. **STATISTICS**: See text portion of the statistical analysis plan for information on inferential statistics for comparisons between IOL group

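### The synopsis hypothesises comparable symptom rates, Section 3 only a comparison, and the readable per-group analysis cannot confirm comparability

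*Protocol*

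**What the plan says.** The protocol words its clinical hypothesis in two ways. In the synopsis, the rate of bothersome visual symptom items in the higher-cylinder "group will be comparable to that of the lower-cylinder" group, which predicts a result. In Section 3 the rate for the "Symfony Toric IOL higher-cylinder group will be compared to the rate for the lower-cylinder group", which describes an activity and predicts nothing.

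The synopsis data analysis section announces a between-group look: "The primary endpoint results will be compared between higher-cylinder toric IOL subjects and lower-cylinder toric control IOL subjects at the 6-month visit". What it then specifies is per group: "The frequency, proportion and 95% Confidence Interval (CI) will be reported for higher-cylinder and lower-cylinder control subjects". It adds: "Descriptive statistics will be used for reporting results".

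Protocol 21.2 and SAP 4 follow the same pattern for the two primary endpoints: frequency, proportion and a two-sided 95% confidence interval at 6 months. Protocol 21.5 and SAP 7 justify the sample size by the precision of a single rate ("With a sample size of 240 subjects and assuming a 20% rate of bothersome visual symptoms or difficulty with an activity due to visual symptoms").

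The readable text contains no margin, no significance level or power for the comparison, no interval for the difference, and no rule for concluding comparability. The table listing in SAP Appendix I directs the reader elsewhere: "See text portion of the statistical analysis plan for information on inferential statistics for comparisons between IOL group". The readable SAP text has no such material.

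**The concern.** A hypothesis that two rates are comparable can be confirmed only against a stated limit on how large an excess still counts as comparable. Two separate rates with their own intervals supply neither that limit nor the quantity to set against it, which is the difference.

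If the synopsis wording stands, someone writing the report must decide after seeing the data whether the hypothesis was met. The informal habits in that position are to note that the intervals overlap or that a test was not significant. Neither shows comparability, and both lean towards finding no problem when a real excess exists. The study's purpose is to compare bothersome symptoms between the higher- and lower-cylinder lenses and to ensure their continued safety, so that lean runs in the less cautious direction.

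**Working it through.** **Inputs.** 240 evaluable subjects per group and an assumed 20% rate for either primary endpoint (Protocol 21.2 and 21.5, SAP 7). The true higher-cylinder rates of 25% and 30%, the observed counts in step 3 and any margin are my assumptions; the documents give none.

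**1. The plan's own figure.** Half-width of a two-sided 95% interval for one rate: 1.96 × √(0.20 × 0.80 / 240) = 1.96 × 2.58 = 5.06 points. The plan states 4.2, which fits a 90% interval (1.645 × 2.58 = 4.25). That discrepancy is a separate matter. What counts here is that the calculation concerns one group, so it sets no limit on the difference.

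**2. Precision of the difference.** Standard error = √(2 × 0.20 × 0.80 / 240) = 3.65 points. The 95% half-width is 1.96 × 3.65 = 7.2 points.

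**3. An observed example.** Take a control result of 48/240 (20.0%).
- At 66/240 (27.5%) the difference is +7.5 points, with a Wald 95% interval of −0.1 to +15.1.
- The first count whose interval for the difference excludes zero is 67/240 (+7.9 points).
- The two separate Wald 95% intervals keep overlapping until 75/240 (31.25%, +11.25 points).

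**4. How often informal criteria would suggest no difference.** Exact binomial enumeration over both groups, 240 each, control rate 20%:

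| True higher-cylinder rate | Separate 95% Wilson intervals overlap | Two-sided 5% pooled z-test not significant |
|---|---|---|
| 25% (+5 points) | 93% | 74% |
| 30% (+10 points) | 59% | 28% |

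**5. What margin this size could support, if one were wanted.** With equal true rates of 20% and one-sided 2.5%, margin = (1.96 + z for power) × 3.65:
- 80% power: (1.96 + 0.84) × 3.65 = 10.2 points.
- 90% power: (1.96 + 1.28) × 3.65 = 11.8 points.

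For a common rate between 10% and 30%, the 80%-power margin runs from 7.7 to 11.7 points.

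These figures are per endpoint. At a 10-point margin, power for one endpoint is 78%. If both endpoints had to pass, joint power would be about 0.78 × 0.78 = 61% if they were independent, and no more than 78% if they coincided.

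**6. Dependence on the margin.** With a true 5-point excess, the chance that the upper limit of the Wald 95% interval for the difference falls below the margin is 3% for a 5-point margin, 26% for 10 and 75% for 15. A wider margin is bound to be easier to pass. The result shows only that *comparable* has no fixed meaning until the margin is stated.

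**The case against.** Three arguments carry weight.

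**Redaction.** Both hypothesis sentences have gaps, the justification of study design in Protocol 4 is empty, the SAP analysis population section breaks off in mid-sentence, and SAP numbering goes from 5.5 to 7. The Appendix I pointer fits hidden inferential text as well as it fits missing text. A reader might infer that the plan has no margin or rule at all; the documents do not support that, because one could sit under a redaction. The gaps do not remove the mismatch between the synopsis and Section 3, since the operative words are legible in both.

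**A descriptive study.** The readable plan is descriptive, and a study with no planned test needs no alpha, power or pass mark. The heading says clinical hypothesis, not statistical hypothesis. This stands, and it is the reason to bring the synopsis down to Section 3 rather than to add a test. It does not rescue a prediction that the described analysis cannot confirm.

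**Conjectured harm.** No passage says that comparability will be declared, or that overlap or non-significance will be the criterion. Both rates and their intervals will be reported, so an excess would be visible. A reader might infer that the plan lets an important excess pass as comparable. The documents do not support this either: they define no important excess, and the 59% and 28% describe criteria that the plan does not state. Those figures show only what would follow if the gap were filled informally.

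**Conclusion.** The point holds as a mismatch between hypothesis and analysis. The synopsis predicts comparability, Section 3 does not, and the readable analysis yields two separate rates with intervals sized on one group's precision. That output cannot confirm the synopsis hypothesis.

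The size rests on 240 per group and a 20% control rate. The difference would be known to about ±7.2 points if both rates are 20%. Used informally, overlap would appear in 59% of studies, and non-significance in 28%, when the true excess is 10 points.

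Two limits apply. The conclusion concerns readable text only. And the groups are non-randomized and open-label, so an unadjusted difference, even one inside a stated margin, would remain open to confounding.

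The rates will be reported either way. What is undefined is the conclusion that may be drawn from them, and that should be settled in wording before database lock.

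**What to change.** Make three wording changes together:

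1. Replace the synopsis hypothesis with the Section 3 wording.
2. State in Protocol 21.2 and SAP 4 that the study estimates the higher-minus-lower difference in rates, with its two-sided 95% confidence interval, for each primary endpoint. Without this, change 1 leaves a comparison with no comparative estimate.
3. State in the same sections that overlapping intervals or a non-significant difference will not be reported as showing comparability.

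None of these needs a margin. If the sponsor keeps *comparable*, or a rule already exists in redacted text, the margin and rule should be stated before database lock. The statement should say whether the rule covers one endpoint or both, since the readable hypothesis names only the symptom items while Section 6.1 says "The primary co-endpoints are the rate of bothersome visual symptoms and the rate of difficulty with an activity due to the symptoms". It should also record that 240 per group supports about 10 points at 80% power per endpoint at a 20% rate, that joint power is lower if both must pass, and that the comparison is non-randomized.

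The cost is text in the synopsis, Protocol 21.2 and SAP 4, plus one extra estimate per endpoint from data already collected. No subjects or visits are added. The downside is that the sponsor gives up an undefined claim of comparability.

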4. STUDY DESIGN

This study is a prospective, multicenter, bilateral, non-randomized, open-label, comparative, 6-month clinical study conducted at up to 50 sites in the USA. Subjects who meet the inclusion/exclusion criteria will be bilaterally implanted with Symfony IOLs, with either 1) Model ZXT300 or ZXT375 IOLs (higher-cylinder group), or 2) control Model ZXT150 (lower-cylinder control group) IOL, implanted in at least one eye, according to the TECNIS Symfony Toric IOL calculator. The fellow eye will be allowed to have any Symfony IOL implanted, according to the TECNIS Symfony Toric IOL calculator, provided it is the same or a lower toric power as the primary eye. The eye with the highest toric power IOL will determine the model group.

JUSTIFICATION OF STUDY DESIGN

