- Documentation of the TECNIS Symfony Toric IOL calculator choice of ZXT toric power for each eye and corresponding residual refractive cylinder and axis, as well as documentation of inclusion of the optional posterior corneal astigmatism algorithm

• PRVSQ Subject Questionnaire (Appendix B)

LENS POWER CALCULATIONS AND IOL SELECTION:

In order to verify subject eligibility and to optimize toric IOL selection and axis placement,

[figure not shown]
investigators will use the web-based TECNIS Symfony Toric IOL calculator (www.TecnisToricCalc.com) to determine the appropriate IOL model for each eye. Note that the TECNIS Symfony Toric IOL calculator provides toric IOL options based on predicted astigmatism, i.e., the vector sum of pre-existing corneal astigmatism and the expected effect of SIA. For this study, subjects are to have corneal astigmatism in at least one eye that, when taking SIA into account and using the PCA algorithm, has approximately 2.00 D to 3.00 D (higher-cylinder group) or 1.00 D to 1.50 D (lower-cylinder group) of corneal astigmatism to be corrected, and subjects must qualify for implantation of the suitable toric IOL by the TECNIS Symfony Toric IOL calculator.

Predicted residual refractive cylinder must be ≤ 0.50 D for all toric eyes. For all subjects, the IOL model selections chosen by the investigator via the TECNIS Symfony Toric IOL calculator are to be printed and maintained as source documentation.

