## 4 POSTOPERATIVE ANALYSES – PRIMARY ENDPOINTS

There are two primary endpoints for this study, rate of bothersome visual symptoms and rate of difficulty with an activity due to the symptoms at 6-month postoperative.

The first primary endpoint is the rate of bothersome visual symptoms,

The second primary endpoint is the rate of reported difficulty with an activity due to one or more visual symptoms, determined by a

"Yes" response to the question "Is there anything you have a lot of difficulty with, or do not do, because of [visual symptom]") at 6 months postoperative.

The frequency and proportion of subjects with bothersome visual symptoms and the frequency and proportion of subjects reporting difficulty with an activity due to one or more visual symptoms will be reported along with the two-sided, 95% confidence interval at the 6-month visit.

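### In the readable plan, the non-randomised comparison of the two primary endpoints rests on crude 6-month rates and makes no use of the preoperative PRVSQ

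*Protocol*

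**What the plan says.** Protocol section 4 describes a "prospective, multicenter, bilateral, non-randomized, open-label, comparative, 6-month clinical study". Groups follow from the toric calculator: about 2.00 to 3.00 D of corneal astigmatism leads to the higher-cylinder lenses and about 1.00 to 1.50 D to the control lens. For a patient with two different lenses, "The eye with the highest toric power IOL will determine the model group".

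The purpose is comparative. The synopsis hypothesis expects the higher-cylinder rate to be comparable to the control rate, and the synopsis data analysis says "The primary endpoint results will be compared between higher-cylinder toric IOL subjects and lower-cylinder toric control IOL subjects at the 6-month visit". The statistics it then names are these: "The frequency, proportion and 95% Confidence Interval (CI) will be reported for higher-cylinder and lower-cylinder control subjects". SAP 4 matches: "The frequency and proportion of subjects with bothersome visual symptoms and the frequency and proportion of subjects reporting difficulty" with an activity "will be reported along with the two-sided, 95% confidence interval at the 6-month visit". Protocol 21.2 reads the same way.

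The list of preoperative tests in Protocol 11.3 closes with "PRVSQ Subject Questionnaire (Appendix B", and 11.6 repeats the questionnaire at 1 and 6 months. The baseline characteristics that SAP 3.2 tabulates by group are age, sex, race and eye colour. Preoperative PRVSQ is not among them.

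**The concern.** Nothing in the design balances the groups on anything other than shared eligibility criteria. Halos, glare and starbursts, and the readiness to report them, can be present before surgery. The outcome is self-reported in an open-label study. A crude difference in 6-month rates therefore mixes any lens effect with differences in prior symptoms, reporting style, age and site.

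The error can go either way. For a post-approval safety question, the costlier outcome is a lens effect that baseline differences cancel, so that the groups appear comparable. A confidence interval conveys sampling error only and gives no warning of this. The preoperative PRVSQ is the most direct baseline measure available, and the readable analysis does not use it.

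**Working it through.** **Inputs from the documents.** Assumed rate 20% and 240 evaluable subjects per group (Protocol 21.2 and 21.5, SAP 7); up to 50 sites; 480 evaluable subjects in total.

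**The plan's own figure.** The stated half-width for one group is 4.2 points. The two-sided 95% value is 1.96 × √(0.20 × 0.80 / 240) = 5.06 points; 4.2 is close to the result with a multiplier of 1.645 (4.25 points). That mismatch is a separate matter and neither supports nor weakens this point.

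**Precision of the comparison.** The standard error of the difference at 20% in both groups is √(2 × 0.16 / 240) = 3.65 points, so the 95% half-width is 1.96 × 3.65 = 7.2 points.

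**Bias of the crude difference.** Suppose the lens has no effect. Let q be the proportion with preoperative symptoms in the lower-cylinder group, g the excess of that proportion in the higher-cylinder group, and k the ratio of 6-month risk with and without preoperative symptoms. Fix the lower-cylinder rate at 20%. Then

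- risk without preoperative symptoms: r0 = 0.20 / (1 − q + q·k); risk with them: r1 = k·r0
- expected crude difference: b = g × (r1 − r0)
- chance that the 95% interval excludes zero: 1 − Φ(1.96 − b/s) + Φ(−1.96 − b/s), where s is the standard error of the difference at the two resulting rates.

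The documents give none of q, g or k. The assumed range is q = 30% or 50%, g = 5, 10 or 20 points, and k = 1.5, 2 or 3. Selected results:

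| q | g | k | r0 | r1 | Bias (points) | Interval excludes 0 (nominal 5%) |
|---|---|---|---|---|---|---|
| 50% | 5 | 1.5 | 16.0% | 24.0% | 0.4 | 5.1% |
| 30% | 10 | 2 | 15.4% | 30.8% | 1.5 | 7.0% |
| 30% | 20 | 2 | 15.4% | 30.8% | 3.1 | 13.0% |
| 30% | 20 | 3 | 12.5% | 37.5% | 5.0 | 26.0% |

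The first and last rows are the smallest and largest of the 18 combinations.

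**Masking.** Take a true lens effect of +5 points, q = 30%, and a baseline gap in the opposite direction. With a 10-point gap and k = 2, the crude difference is 5 − 1.5 = 3.5 points. With a 20-point gap and k = 3, it is 5 − 5 = 0.

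**Effect of standardising.** In these scenarios the risks within each baseline stratum differ between groups only by the lens effect. Comparing both groups on a common baseline distribution therefore removes the bias entirely. This holds by construction, because preoperative symptoms are the only confounder in the model.

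**Feasibility.** Expected events are 0.20 × 480 = 96, enough for a small model. Fifty sites would average 480 / 50 = 9.6 subjects and 96 / 50 = 1.9 events each, too few for a separate term per site.

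**The case against.** A fair defence has four parts.

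- **Hidden text.** The readable text is incomplete where an adjusted analysis might sit. Protocol 21.1 loses part of a sentence on additional primary-endpoint analyses, SAP 2.1 breaks off where it turns to the final report, SAP numbering goes from 5.5 to 7, and SAP Appendix I refers to inferential group comparisons that no readable section contains. This stands. A reader might infer that the sponsor has decided against adjustment; the documents do not show that.
- **Descriptive plan.** The sample size rests on single-group precision, and no readable text gives a between-group contrast or margin. Adjustment would thus refine a contrast that itself still has to be written. This is true, but the plan does say the groups will be compared, and the adjustment should be fixed when the contrast is.
- **Existing safeguards.** SAP 3.1 and 3.2 tabulate enrolment by site and demographics by group, no site may exceed 25% of enrolment, and eligibility is common to both groups. SAP 5.3 tabulates questionnaire items without naming a visit, although SAP 2.1 points to 6 months. These steps may limit or reveal imbalance but do not correct for it.
- **Weak carry-over.** Preoperative symptoms partly reflect the cataract and uncorrected astigmatism that surgery treats. They may predict 6-month bother weakly, or mean different things in the two groups. This stands as a limit on how much bias adjustment can remove.

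**Conclusion.** The point holds for the readable text: a non-randomised comparison is planned on crude 6-month proportions, although the PRVSQ is also given before surgery, and no readable section adjusts for baseline symptoms or tabulates them by group. It is worth correcting, but it does not show that the result will be wrong.

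The size is unknown. Under the assumed ranges it is about 0.4 to 5 points on a 20% rate, with a middle case of about 1.5 points, small beside the 7.2-point half-width of the difference. Reaching 5 points needs a large baseline gap and strong prediction together.

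Two stronger inferences are not supported. One is that the crude comparison is known to be materially biased; the documents contain no baseline rates from which to say so. The other is that adjustment would isolate the effect of lens cylinder. Corneal astigmatism essentially defines the groups, so the two effects cannot be separated. The ranges are approximate and allow for surgically induced and posterior corneal astigmatism, so raw keratometric values may overlap at the edges, but not enough to rescue that interpretation.

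**What to change.** If a blacked-out section already contains an adjusted analysis, the sponsor need only confirm it and check it against the items below. Otherwise, in SAP 4:

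1. Keep the crude rates and their confidence intervals.
2. Add, for each primary endpoint, a pre-specified standardised risk difference with a 95% confidence interval. Adjust for the preoperative PRVSQ response to the same halo, glare and starburst items and for age. Handle site as a random effect or in pooled strata defined in advance, not as up to 50 separate terms.
3. Tabulate preoperative PRVSQ by group, and 6-month rates by preoperative symptom status. The second table will show whether the carry-over assumption has any force.
4. Word the conclusion as applying to patients who receive higher-cylinder lenses.

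The questionnaire form is not readable, so the sponsor should first confirm that the preoperative version carries the same bother and difficulty items; where it does not, use the nearest available item and say so.

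The cost is SAP wording, one model per endpoint and two tables, with no new visit, procedure or subject. The SAP should state the downsides: the estimate is model-based, and preoperative symptoms are an imperfect measure because they partly reflect cataract and uncorrected astigmatism.
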